- When the UMass RA finds a study ID with the completed **Informed Consent instrument** (i.e., green color), the RA refers to **random_group_assign.xlsx** (in the Google folder **Pre-determined randomization, which is only available to the UMass RAs**) and assigns the study ID to either Group A or B.

- **Group A**
 - First period: Neuro-World game intervention (12 weeks)
 - Second period: phone interaction + usual care (12 weeks)
- **Group B**
 - First period: phone interaction + usual care (12 weeks)
 - Second period: Neuro-World game intervention (12 weeks)

- **The Randomization instrument** will be hidden from the Rutgers personnel throughout the study.

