
Highest level privileges:
 
Project Design and Setup 
 
User Rights 
 
Data Access Groups 
 
Privileges for data exports (including PDFs and API exports), reports, and stats:
 
Data Exports
 
* De-identified means that all free-form text fields will be removed, as well as any date/time fields and Identifier fields.
 
No Access 
 
De-Identified* 
 
Remove all tagged Identifier fields 
 
Full Data Set 
 
Add/Edit/Organize Reports 
 
Also allows user to view ALL
	
This privilege has no effect on data imports or data exports.
 

	No Access (Hidden)	Read Only	View & Edit	

Volunteer Demographics				

Screening Data				

Screened Result				

Informed Consent				

Randomization Form				

Baseline Data				

12-Week Follow-up Data				

24-Week Follow-up Data				

		No Access (Hidden)	Read Only	View & Edit	Volunteer Demographics				Screening Data				Screened Result				Informed Consent				Randomization Form				Baseline Data				12-Week Follow-up Data				24-Week Follow-up Data			

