	No Access (Hidden)	Read Only	View & Edit																																		
Volunteer Demographics																																					
Screening Data																																					
Screened Result																																					
Informed Consent																																					
Randomization Form																																					
Baseline Data																																					
12-Week Follow-up Data																																					
24-Week Follow-up Data																																					

5. Assessment at baseline (Only Rutgers RA can perform assessment; UMass RAs will organize the overall meeting)

- A UMass RA will remind the participant of the scheduled assessment.
 - Give a call to the participant, remind them 1 day before the scheduled assessment in the following order.
 - Phone call
 - If not answering, text and email.
 - Give a call to the participant, remind them 2 hours before the scheduled assessment.
 - Phone call
 - If not answering, text and email.
- A UMass RA will organize the zoom meeting.
 - The UMass RA will initiate a zoom meeting.
 - A UMass RA will email a zoom link to the participant's email and the Rutgers RA approximately 10 minutes before the scheduled time.
 - The Rutgers RA will join the meeting.
 - Introduce RAs
 - Message: "*Hello, [Participant name]. I am [Umass RA name], and a researcher from UMass Amherst. Today, we will administer cognitive assessments and some surveys to you and your helper. They will take about 2 hours to complete. All the assessments will be administered by [Rutgers RA]. Can you introduce yourself briefly, [Rutgers RA]? Before starting assessments, I will break a room for [Rutgers RA] to give some important instructions for today's session.*
 - The UMass RA will break out a meeting room for the Rutgers RA, and the Rutgers RA will wait in the room.

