 - The volunteer will join the meeting at the scheduled time.
 - The UMass RA will explain about the assessment.
 - Message:
 - Group A: "*OK. I will give the overall process of our study first. Our study participants are divided randomly into Group A/B. You are selected as Group A. It means that for the first 12 weeks, you play a cognitive game with the provided tablet PC. We will also follow up on your game playing experience and your cognitive and physical activity by call and email survey. They will be very brief and take about 1 min. After 12 weeks, you need to return a table PC, and do the second assessment, and don't need to do anything particular for the next 12 weeks. We will just check your cognitive and physical activity. For this assessment, an important note is that [Rutgers RA] should not know about which group you are in. Please know that [Rutgers RA] is only here for the assessment purpose. To assess your cognitive function without any bias, [Rutgers RA] should not know which group you are in, you already received a table PC, and start to play a game soon. So, if you have any concerns or questions related to our overall study procedure, game play or tablet PC, please feel free to talk to me or ask me. {optional} For today's assessment, [Helper Name] will be asked survey questions related to [participant name]'s daily activity first before starting cognitive assessment. I will break a zoom room for [participant name] during the survey, and let [participant name] join again after completing the survey. [participant name], do you feel comfortable with using zoom? After completing the survey, [helper name] please stay in the house but not in the room during the assessments.} The entire assessment will be video-recorded for future reference. Now the [Rutgers RA] will join and start the assessment. I will stay muted until the assessment is over, but if you have a question, please feel free to ask me.*

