- Group B: “OK. I will give the overall process of our study first. Our study participants are divided randomly into Group A/B. You are selected as Group B. It means that For the first 12 weeks, you don’t need to do anything for this study but we will just check you about your cognitive and physical activity such as puzzles, board games or hiking like that. After 12 weeks, you will receive a table PC and play a cognitive training game. For this assessment, an important note is that [name] should not know about which group you are in. *Please know that [name3] is only here for the assessment purpose. To assess your cognitive function without any bias, [Rutgers RA] should not know that you are starting 12 weeks with no game play and you will receive a table PC 12 weeks later. So, if you have any concerns or questions related to our overall study procedure, game play or tablet PC, please feel free to talk to me or ask me. {(optional) For today's assessment, [Helper Name] will be asked survey questions related to [participant name]'s daily activity first before starting cognitive assessment. I will break a zoom room for [participant name] during the survey, and let [participant name] join again after completing the survey. [participant name], do you feel comfortable with using zoom? After completing the survey, [helper name] please stay in the house but not in the room during the assessments.} The entire assessment will be video-recorded for future reference. Now the [Rutgers RA] will join and start the assessment. I will stay muted until the assessment is over; but if you have a question, please feel free ask to me.”*”
-
- The UMass RA will bring the Rutgers RA back to the main meeting room and start **recording the assessment**.
- Five different **Assessment Form (1-5) instruments** have a different randomized order of tests. RAs select an assessment form using **Assessment/Assessment Form Assignment.xlsx** in Google drive. Then, the questions and fields of the selected **Assessment Form instrument** will appear.
- The Rutgers RA will administer all the assessments and enter all answers to **the corresponding Assessment Form instrument**. The Rutgers RA will score the participant as he/she administers the assessments.

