- A UMass RA will ship a tablet computer, a return label, and a hardcopy instruction for returning the tablet computer to the participant's address.

- The UMass RA will generate the shipping label using the UMass paying account (**F2E075**) and the participant's address stored in **the Address to ship the tablet computer field of the MCI Participant Demographics instrument**.
 - <https://www.easyship.com/blog/prepaid-return-labels>
 - <https://www.ups.com/us/en/campusship-support/return-services.page>
- The UMass RA will generate the returning label.
- The UMass RA will perform a factory reset on a tablet computer to be shipped.
- The UMass RA will perform all the updates.
- The UMass RA will install Neuro-World.
- The UMass RA will enter the study ID in Neuro-World.
- The UMass RA will double-check to make sure Neuro-World works as expected.
- The UMass RA will print out the instructions.
- The UMass RA will wrap the tablet + plastic case in a bubble wrap, put it in the air-inflated laptop package, and put it in the box.
- The UMass RA will put the printed instructions and the returning label in the box.
- The UMass RA will seal the box using scotch tape.
- The UMass RA will put a shipping label on the box and place it in the on-campus UPS pick-up location.
- The UMass RA will text and email both the participant and the caregiver about the estimated delivery date.
- The UMass RA will enter the shipped date, and the tracking number in **the Shipped Date field** (both **Shipping to the subject from the UMass**, **Returning to the UMass from the subject**) of **the Tablet Ship & Return instrument**.

- A UMass RA will track the delivery of the tablet computer.

- The UMass RA, on his/her assigned date, will check if any of the tablet computers are estimated to have arrived.
- The UMass RA tracks the delivery using the tracking number.
- If the package is reported to be delivered,
 - The UMass RA will call the participant (the caregiver if the participant cannot be reached) and confirm the delivery.
 - If the participant (or the caregiver) confirms the receipt of the tablet computer,
 - The UMass RA will schedule a tutorial session when the participant, the caregiver, and one UMass RA are available based on the Google calendar.
(AHHA lab account, [contact])
 - The UMass RA will notify the responsible UMass RA for the tutorial (the UMass RA, who schedules the tutorial session, may not be the one who is available for the tutorial session).

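### The REDCap rights screen hides the Randomization form from data entry only, and no text hides the tablet shipping form, so an avoidable route to the group remains open to the sole outcome rater

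*Protocol*

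**What the plan says.** **The rule.** Protocol section 4 gives randomisation to the UMass RAs and says that the Randomization instrument "will be hidden from the Rutgers personnel throughout the study".

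**The screen.** The rights screen that follows sets the Randomization Form to No Access (Hidden) and every other listed form to View & Edit. Of the form-level setting it says: "This privilege has no effect on data imports or data exports". A separate block is headed "Privileges for data exports (including PDFs and API exports), reports, and stats". There, Data Exports is at De-Identified, and the box for adding and editing reports is ticked. A footnote defines the export level: "De-identified means that all free-form text fields will be removed, as well as any date/time fields and Identifier fields". User Rights and Project Design and Setup are ticked under the highest-level privileges.

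**The rater.** The heading of section 5 reads "Only Rutgers RA can perform assessment; UMass RAs will organize the overall meeting". The Rutgers RA scores while testing. Sections 9 and 12 repeat the procedure at weeks 12 and 24.

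**The shipping form.** Section 6: "The UMass RA will enter the shipped date, and the tracking number in" the Tablet Ship & Return instrument. The section 5 script for Group B says "After 12 weeks, you will receive a table PC and play a cognitive training game"; Group A gets the tablet around baseline.

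**The test.** SAP section 2 plans paired t-tests of the intervention against the non-intervention period, one-sided at 0.05.

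**The concern.** The rule promises that Rutgers staff will not see the allocation in REDCap. The setting shown to deliver it governs only whether the form can be opened for data entry. Exports, reports and the right to manage user rights are separate privileges, and on this screen all are on. The rule also names one instrument, although another form records a date that tells the groups apart.

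This matters because one person administers and scores every outcome at every visit. MoCA, MMSE and digit span leave some room for judgement and prompting. If the rater knew the group, scores could drift toward the hypothesis, and a one-sided test would count that drift as benefit. The protocol says "The entire assessment will be video-recorded for future reference", so blinded re-scoring would be possible, but none is planned in the text provided. No check of rater blinding is described either.

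**Working it through.** The plan states no figure to reproduce. The check sets the rule beside the screen and the forms; the arithmetic at the end is illustration only.

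**1. Does the setting deliver the rule?**

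| Route to the group | What the screen shows | Closed? |
|---|---|---|
| Open the Randomization Form | No Access (Hidden) | Yes |
| Export the data | Form setting does not apply; De-Identified export on | Only if the group field is free text or tagged as an identifier |
| Build a report | Ticked; the sentence on its scope is cut off in the text | Not shown to be closed |
| Change the rights | User Rights and Project Design and Setup ticked | No, but it would take a deliberate act |

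De-Identified export drops three kinds of field: free text, date/time and identifiers. A coded A/B field is none of these unless tagged. The documents do not give the field type, its tagging, or whether the study ID is exported. The export route is therefore possible, not proven.

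**2. Whose screen is it?** No role is named. It follows the rule directly and hides only the form that the rule names. Hiding that form from the UMass RAs, who randomise, would make no sense. It most likely shows the Rutgers role. Its form names (for example Volunteer Demographics) differ from those in the text (MCI Participant Demographics), so it may be an earlier build.

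**3. Does the shipping date reveal the group?** The documents disagree on when Group A receives the tablet. The section 5 scripts speak of it as already received or sent. The procedure list puts shipping after the baseline assessment, and section 5 records the address at the end of that visit. On either reading Group A's tablet ships at about baseline and Group B's after week 12. A shipping entry in the first 12 weeks therefore points to Group A. As a date field it would drop out of a De-Identified export, so the exposure is viewing the form. It is absent from the screen, and no text hides it.

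**4. Illustrative size.** All inputs except n = 50 (protocol section 1) and the one-sided 0.05 are assumed: MoCA SD 2.5, equal correlation r = 0.7 between visits, drift d once the rater knows training has occurred, and share p of participants unblinded.

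- Paired difference: ±(2·Y12 − Y0 − Y24), with SD = SD·√(6(1 − r)) = 2.5·√1.8 = 3.354. SE = 3.354/√50 = 0.474.
- Drift after training affects weeks 12 and 24 in Group A (2d − d = d) and week 24 in Group B (d). The mean shift is d·p; the variance gains d²·p(1 − p).
- Type I error from the noncentral t distribution, 49 df, rechecked:

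| Share unblinded | d = 0.25 | d = 0.5 |
|---|---|---|
| 10% | 5.6% | 6.2% |
| 20% | 6.2% | 7.5% |
| 50% | 8.3% | 13.0% |
| 100% | 13.0% | 27.2% |

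Over SD 2 to 3 and r 0.6 to 0.8 (SE 0.310 to 0.657), the 20% row runs from 5.8% to 6.9% and from 6.7% to 9.2%. The 100% row is included because one export could show every record; at p = 1 the shift is simply d and the variance term vanishes.

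**The case against.** The strongest reply is that an unlabelled, possibly outdated image should not outweigh a clear written rule, and that the plan does not rely on this control alone. The allocation file sits in a folder open only to UMass RAs. The rater waits in a breakout room during the group briefing and leaves before the schedule is discussed. The scripts tell participants that the rater must not learn their group. The role table gives Rutgers no part in shipping, tutorials, compliance calls or tablet return. No section gives Rutgers an export or report task.

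All of that stands, and it limits the weight of the point. It does not remove it: the only access settings the protocol shows do not do what the rule says, and the gap for the shipping form does not depend on the screen.

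Three stronger readings are not supported.

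- A reader might infer that the rater is or was unblinded. The documents do not show this.
- A reader might take the screen as the live rights of the rater's own account. It names neither role nor user.
- A reader might add that the rater's weekly check of the lab email and voicemail (section 2) would expose group information. That is a screening task. Sections 5 and 7 direct participants' questions to the UMass RA, and contact details are removed from the text, so a separate route may exist. It is not part of this point.

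**Conclusion.** The point holds as a cheap improvement. As printed, the REDCap control hides the Randomization form from data entry but not from exports, reports or a change of rights, and nothing hides the shipping form. This is a stated setting that falls short of a stated rule, affecting the only outcome rater.

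It rests on two inferences: that the screen shows the Rutgers role, and that the group is held as a coded, untagged field. The shipping-form gap needs neither. The effect on the results is unknown. The type I error figures show only which way a bias would run and how it would scale under assumed inputs, and they should not be read as an estimate for this trial.

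**What to change.** For the Rutgers role in REDCap:

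- set Data Exports to No Access or, failing that, tag the group field as an identifier so that De-Identified export drops it;
- untick report building, User Rights, and Project Design and Setup;
- set Tablet Ship & Return to No Access, and Weekly Follow-up as well. The latter is a precaution: section 8 describes only call dates and whether contact was made, in both periods, but any notes on training would show the period.

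Extend the rule in section 4 to name these forms. Replace the screen with a current one labelled with its role, and reconcile the statements on when Group A's tablet is shipped. Optionally, record the rater's guess of group at weeks 12 and 24.

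The cost is a change of role settings, a new screenshot and, if adopted, one extra item at two visits. The downside is that UMass must run any export that Rutgers needs. If the live rights are already tight, only the labelling and the text change.

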 - **(Videoconference version)** Montreal Cognitive Assessment (**MoCA**): Chapman, J. E., Cadilhac, D. A., Gardner, B., Ponsford, J., Bhalla, R., & Stolwyk, R. J. (2019). Comparing face-to-face and videoconference completion of the Montreal Cognitive Assessment (MoCA) in community-based survivors of stroke. *Journal of telemedicine and telecare*, 1357633X19890788.
 - **(Videoconference version)** Mini-Mental State Examination (**MMSE**): Timpano, F., Pirrotta, F., Bonanno, L., Marino, S., Marra, A., Bramanti, P., & Lanzafame, P. (2013). Videoconference-based mini mental state examination: a validation study. *Telemedicine and e-Health*, 19(12), 931-937.
 - **(Original)** Digit Forward Span (**DFS** from WAIS-IV): Powell, D. H., & Hiatt, M. D. (1996). Auditory and visual recall of forward and backward digit spans. *Perceptual and Motor Skills*, 82(3_suppl), 1099-1103.
 - **(Original)** Digit Backward Span (**DBS** from WAIS-IV): Powell, D. H., & Hiatt, M. D. (1996). Auditory and visual recall of forward and backward digit spans. *Perceptual and Motor Skills*, 82(3_suppl), 1099-1103.
 - **(Original)** Geriatric Depression Scale (**GDS**)
 - **(Original)** Short Form 36 (**SF-36**)
 - **(Original)** Alzheimer’s Disease Cooperative Study/ADL scale adapted for MCI participants (**ADCS/MCI/ADL24**)
- When the Rutgers RA completes the assessments, he/she will message the UMass RA in the smart phone texting group.
- The UMass RA will unmute.

- The Rutgers RA will leave.
- The UMass RA enters the address in **the Address to ship the tablet computer field of the MCI Participant Demographics instrument.**
- The UMass RA will inform the participant about the assignment result and explain the schedule.
 - Group A

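### Participants, and any helper, learn their group just before the baseline tests; moving the disclosure after the tests avoids this at almost no cost

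*Protocol*

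**What the plan says.** Protocol section 4 makes completed consent the trigger for allocation: "When the UMass RA finds a study ID with the completed" consent form, that RA looks up the group. Baseline is the next step.

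At the baseline meeting (section 5) the assessor is first moved away: "The UMass RA will break out a meeting room for the Rutgers RA, and the Rutgers RA will wait in the room". The UMass RA then reads a group-specific script. One version says "You are selected as Group A. It means that for the first 12 weeks, you play a cognitive game"; the other says "You are selected as Group B" and explains that the game comes after 12 weeks. Where there is a helper, the same script tells the helper that they will answer questions on the participant's "daily activity first before starting cognitive assessment". Each script asks the participant not to reveal the group to the assessor and closes with "Now the [Rutgers RA] will join and start the assessment".

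After the tests, once the assessor has left, section 5 has a further step: "The UMass RA will inform the participant about the assignment result and explain the schedule".

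The assessor is otherwise well protected. The allocation file is open only to the UMass RAs, and the randomisation form "will be hidden from the Rutgers personnel throughout the study".

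SAP section 2 plans paired t-tests of changes between the intervention and non-intervention periods, one-sided at 0.05.

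**The concern.** A baseline should be fixed before anyone who contributes to it knows the allocation. Here the participant hears either that the game starts now or that nothing is required for 12 weeks, and is tested straight afterwards. GDS and SF-36 are self-reported, and the cognitive tests depend on effort, so mood, motivation or expectation could move these scores, possibly differently in the two groups. If baseline is the starting point of the period-1 change, such a difference passes into the treatment contrast and cannot be removed afterwards.

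There is also a masking cost. A person with MCI is told the group and must then keep it from the assessor through a session of about two hours. At this first visit the risk need not exist.

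**Working it through.** **Order of events.** Consent, allocation (section 4), group-specific script, helper survey if there is a helper, tests, assessor leaves, assignment result given (section 5). The group is thus given twice, and the second time would be enough. The closing messages after the tests describe each schedule but do not name the group, so they would need editing to carry the disclosure alone.

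**A second route to the same knowledge.** The Group A opening script says the tablet has already arrived, and the Group A closing message says it was sent. Yet section 5 records the shipping address only after the tests, and shipping is section 6. If tablets do arrive first, moving the script alone would leave Group A aware of its group.

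**Effect on the analysis.** The plan gives no figure to reproduce, so this is an illustration.

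- From the documents: 50 participants (Protocol section 1); paired t-test, one-sided 0.05 (SAP section 2).
- Assumed: 1:1 allocation, no dropout, no true effect, SD 3 (range 2–4), equal correlation ρ = 0.7 between visits (range 0.6–0.8), and an outcome where higher is better.

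Let y0, y1, y2 be the scores at baseline, week 12 and week 24. The intervention-minus-control contrast of period changes is:

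- Group A: (y1−y0)−(y2−y1) = 2y1−y0−y2. A baseline reaction a shifts it by −a.
- Group B: (y2−y1)−(y1−y0), the negative of the above. A baseline reaction b shifts it by +b.

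The mean shift at 25 per group is (25b−25a)/50 = (b−a)/2. Differences b−a of 0.5, 1 and 2 points give 0.25, 0.5 and 1.0 point.

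The contrast variance is SD²(4+1+1) + 2ρSD²(−2−2+1) = 6SD²(1−ρ). So its SD is 3×√1.8 = 4.02, and its SE is 4.02/√50 = 0.569.

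Rejection rates from the noncentral t with 49 df:

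| b−a | shift | rejection rate |
|---|---|---|
| 0 | 0 | 0.050 |
| +0.5 | 0.25 | 0.113 |
| +1 | 0.5 | 0.218 |
| +2 | 1.0 | 0.535 |
| −1 | −0.5 | 0.006 |

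For b−a = +1 the rate runs from 0.140 (SD 4, ρ 0.6) to 0.479 (SD 2, ρ 0.8).

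Simulation (40,000 trials, SD 3, ρ 0.7) agrees: (a,b) = (0,1) gives 0.214, (1,0) gives 0.007, and (1,1) gives 0.046. Pairing end-of-period scores instead (y1 against y2) gives 0.048 to 0.052 in every case, because y0 is not used.

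**Smaller reactions, in SD units (simulated).** If the Group A baseline falls and Group B does not move:

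| Fall in Group A | ρ = 0.5 | ρ = 0.7 | ρ = 0.8 |
|---|---|---|---|
| 0.1 SD | 0.075 | 0.083 | 0.093 |
| 0.2 SD | 0.105 | 0.128 | 0.155 |
| 0.3 SD | 0.147 | 0.191 | 0.241 |

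A rise of 0.2 SD in Group A makes the test conservative, at 0.020 to 0.011 over the same correlations.

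**The case against.** The harm is conditional. It needs a reaction that differs between groups and an analysis based on period changes, and it inflates false positives only in one direction. Nothing in the documents supports a particular size. A one-point difference at SD 3 is a third of an SD, which is a lot to expect from hearing a schedule; at 0.1 SD the error rate rises only to 7.5–9.3%. Both groups eventually receive the game, so the news concerns order rather than access. MoCA, MMSE and digit span are performance tests scored by a masked assessor, and screening supplies a MoCA before allocation. The helper is optional, and the daily-activity scale listed in Protocol section 5 is not the one named in the SAP, so the helper's survey is not shown to feed an analysed outcome.

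All of this bears on weight, and it stands as such: the rejection rates are illustrations, not predictions. It does not touch the order of events. The SAP does not say that the screening MoCA is used, and screening gives no such value for the other outcomes. The closing messages do need rewording, but that is an edit, not an obstacle.

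A further point is that the opening script carries the only warning before the tests not to reveal the group. Once no one has a group or a tablet to reveal at baseline, that warning has no work to do there, though a neutral reminder does no harm.

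**Conclusion.** The concern holds. Baseline is taken with the participant, and any helper present, aware of the allocation, and the protocol already has a later point at which to tell them. The possible bias in the period-change contrast is (b−a)/2 under equal allocation, of unknown size and sign. It is zero if the two groups react equally, and baseline drops out if end-of-period scores are paired. The figure of about 22% for a one-point difference rests on the assumed SD, correlation and 1:1 split.

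The correction protects baseline and removes the slip risk at the first visit only. At weeks 12 and 24 participants necessarily know what they received, so that risk and any lasting expectation effect remain. This should be changed because it is avoidable and cheap, not because a large bias has been shown.

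**What to change.** 1. In Protocol section 4, change the trigger for allocation from completed consent to completed baseline assessment. At the least, withhold the group until the tests are done.
2. In section 5, replace the two opening scripts with one group-neutral script saying that the group will be given after the tests, once the assessor has left. It may include a neutral request to take study questions to the UMass RA.
3. Make the post-test step the only disclosure at this visit. Edit its two messages to name the group, and put the request not to tell the assessor there.
4. Sections 9 and 12 copy the baseline procedure. Give weeks 12 and 24 their own script that keeps that request.
5. Reconcile the statements in section 5 that the tablet has already been sent or received with the address entry after the tests and with section 6, so that a tablet does not reveal the group before baseline.
6. State in SAP section 2 whether the paired test uses period changes or end-of-period scores, since this decides whether baseline enters.

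The cost is a reordering of two steps and script edits, with no added visit, staff or participants. If tablets are in practice shipped before baseline, Group A may start training slightly later. If enrolment is already under way, which the documents do not establish, record which baselines preceded the change.
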